## 11.5 Abnormal CD4 T cell counts

For any CD4 T cell decline of 50% or greater, or if the CD4 T cell count is  $<200/\text{mm}^3$ , the participant will be contacted and asked to return for a repeat test as soon as the participant is available. If repeated

## Protocol

measurements of CD4 T cell counts confirm an absolute CD4 T cell decline of 50% or more relative to baseline (average of screening and pre-entry values) or an absolute CD4 T cell decline below 200/mm^3 cells, the results should be discussed with the study chairs. The chairs will discuss these results with the patient's primary HIV clinician and may decide to continue the study medication with close monitoring of CD4 T cells if the relative CD4 T cell count is  $\leq 5$  percentage points lower from the baseline relative CD4 T cell count.

### 11.6 Adverse reactions due to ART

Any participant experiencing an AE that is attributable to background ART may have the event treated according to recommendations in the package insert(s) of the product(s) or current treatment guidelines. Irrespective of possible causality, all non-serious AEs and SAEs must be recorded in the CRF. All changes to a participant's ART regimen should be discussed with the study co-chairs and must be accurately recorded on the CRF.

### 11.7 Other abnormal laboratory or clinical findings

Abnormal laboratory tests and abnormal clinical findings will be categorized using a standard grading scale described before.

Abnormal laboratory findings (e.g. clinical chemistry, hematology, urinalysis) or other abnormal assessments (e.g. ECGs, X-rays, vital signs) that are judged by the investigators as **clinically significant** will be recorded as AEs or SAEs if they meet the definition of an AE, as defined in Section 10.3.1 ("Definition of an AE"), or SAE, as defined in Section 10.3.2 ("Definition of a SAE"). Clinically significant abnormal laboratory findings or other abnormal assessments that are detected during the study or are present at baseline and significantly worsen following the start of the study will be reported as AEs or SAEs. However, clinically significant abnormal laboratory findings or other abnormal assessments that are associated with the disease being studied, unless judged by the investigators as more severe than expected for the participant's condition, or that are present or detected at the start of the study and do not worsen, will **not** be reported as AEs or SAEs.

Participants with grade 3 and 4 asymptomatic and clinically insignificant laboratory abnormalities may continue to receive cART and remain on the treatment schedule at the investigators' discretion, unless regulated otherwise in Tables 2 to 4.

Any abnormal clinical finding will be reported as an SAE if it meets the criteria defined above.

### 11.8 Antiretroviral treatment failure

HIV treatment failure is defined as a confirmed HIV-1 RNA increase to >400 copies/mL for more than 4 weeks. This level is higher than typical in clinical trials, due to the fact that panobinostat can increase plasma HIV- RNA as a result of increased transcription (not replication).

An increase in viral load to >1000 copies/mL among study participants should be confirmed with repeat testing on samples obtained at least 7 days apart. If there is a confirmed increase to >1000 copies/mL in plasma HIV-1 RNA viral loads in participants on ART, a plasma specimen should be obtained and sent for evaluation of antiretroviral drug resistance. Confirmed HIV-1 relapse specimens must have repeated detection of >1000 copies/mL for successful HIV-1 drug resistance testing.

Clinical management of HIV-1 virologic breakthrough and treatment failure will be handled by the investigators according to current HIV treatment guidelines.

## Protocol

### 12.0 TERMINATION RULES

#### 12.1 Termination rules for individual participants

##### 12.1.1 Participant Withdrawal from Study

Participant withdrawal from study is defined as any participant who does not complete the final follow-up visit or an early termination visit defined in this protocol. Reasons why a study participant does not complete final visits can include:

- Participant request (withdrawal of consent)
- Protocol violation
- Adverse events or reactions
- Any condition, interaction, or contraindication where continued participation in the study will result in an unacceptable risk for the participant, as assessed by the Investigators or advisers
- Discontinuation of the study by the Sponsor
- Lost to follow-up
- Investigator determination in consultation with study co-chairs, e.g. for repeated non-adherence to study protocols

Investigators will contact participants who fail to return for planned visits and if possible schedule a new visit. Information related to study withdrawal is documented in the CRF including the reason for withdrawal, date of withdrawal, and whether the participant or Investigators made this decision. Participants withdrawn from the study will contribute with data for the statistical analyses until the date of withdrawal. Participants withdrawn from the study will resume routine treatment following standard treatment guidelines.

##### 12.1.2 Withdrawal from the investigational drug

Withdrawal from the investigational drug is defined as a participant who discontinues study treatment but agrees to continue follow-up until completion of the study. Any participant who withdraws from the investigational drug after having received at least one dose of study medications will be asked to return for all subsequent study visits. If withdrawal from the investigational drug is due to adverse events, this will be followed up as detailed under 10.7.

Study participant will be withdrawn from the investigational drug in case of the following events:

- Participant request (withdrawal of consent)
- Pregnancy
- Development of a grade 3 or 4 adverse event that is related to the investigational products. Participants with grade 3 or 4 adverse events limited to laboratory abnormalities without clinical signs and symptoms or are clearly attributable to other diseases may be allowed to continue
- Early or delayed hypersensitivity reaction
- Investigator determination in consultation with study co-chairs, e.g. for repeated non-adherence to study protocols
- Termination of the study by the Protocol Safety Monitoring Committee, NIAID, FDA or the pharmaceutical companies providing the investigational agents
- Any condition, interaction, or contraindication where continued participation in the study will result in an unacceptable risk for the participant, as assessed by the Investigators or advisers

## Protocol

Information related to withdrawal from the investigational drug is documented in the CRF including the reason for withdrawal, date of withdrawal, and whether the participant or Investigators made this decision. Participants withdrawn from the investigational drug will contribute with data for the statistical analyses until the date of withdrawal. Participants withdrawn from the investigational drug will resume routine treatment and control at the Department of Infectious Diseases following standard treatment guidelines.

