### 9.3.3 Treatment phase

Study entry will be defined as the day on which the first dose of study drug is administered (day=0, visit V3).

On this day, participants will have the following procedures performed:

- Perform a pregnancy test, ECG and vital signs/physical exam (including eye exam), as described in pre-treatment assessment (9.2.4).
- Review concomitant medications.
- Collect blood for baseline immunologic and virologic assays.
- Perform randomization to treatment Arm A or B or C.
- After the above procedures are completed, administer one s.c. dose of PEG-IFN- $\alpha$ 2a in patients randomized to treatment Arm B and C.
- Immediately after the first administration of PEG-IFN- $\alpha$ 2a, participants will be asked to take the first pill of panobinostat p.o., at the stage-specific dose if randomized to arm A or B.
- At 6h after administration of panobinostat, blood samples will be collected for virological, immunological and pharmacokinetic assays.
- 4-6 hours after administration of panobinostat, at the time of Cmax for panobinostat, a 12-lead ECG will be performed.
- On discharge, participants randomized to stage A or B will receive two more stage-specific panobinostat doses and will be instructed to take them in the mornings of study day 2 and day 4.

On Day 2, participants will be called by phone by one of the study investigators to discuss possible side effects. Participants will return on Day 4, six hours after administration of the third dose of panobinostat (visit V4), for collection of blood samples for virological, immunological and gene expression studies, as described in Table 1, and for an ECG. The full volume of blood to be collected on day 4 will only be collected if the most recently available hemoglobin level is  $\geq 12.0$  g/dL for men and hemoglobin  $\geq 11.0$  g/dL for women.

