### 9.5 Early termination visit

Any participant who discontinues study treatment prematurely should be encouraged to continue to participate in all scheduled visits.

A participant may voluntarily discontinue participation in this study at any time. The investigator may also, at his or her discretion, discontinue the participant from participating in this study at any time. If a participant is prematurely discontinued from participation in the study for any reason, the investigator must make every effort to perform the following evaluations:

- Perform clinical evaluation.
- Review adverse events and concomitant medications.
- Obtain samples for laboratory tests:
  - Hematology (CBC/differential), Chemistry testing.
  - HIV RNA testing by Roche Taqman Version 2.0 assay.
  - CD4 T cell counts.
  - Collection of blood samples for virological and immunological assays.

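### Section 12.1.2 stops using data at drug withdrawal, which discards day-10 primary endpoint values that the plan collects and 14.4.3 would analyse; the exclusion in 14.4.3 also lacks a time limit

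*Combined protocol and SAP*

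**What the plan says.** **Follow-up after stopping drug.** Section 12.1.2 defines withdrawal from the investigational drug as stopping treatment while agreeing to stay in follow-up. It says that anyone who has had at least one dose "will be asked to return for all subsequent study visits". Section 9.5 agrees: "Any participant who discontinues study treatment prematurely should be encouraged to continue to participate in all scheduled visits".

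**Use of their data.** Section 12.1.2 then adds: "Participants withdrawn from the investigational drug will contribute with data for the statistical analyses until the date of withdrawal".

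**Primary efficacy set.** Section 14.4.3 uses a modified intention-to-treat set: at least one dose of randomized treatment, with baseline and day-10 data. Its next sentence excludes those who go off ART, have virologic failure or discontinue participation, and names no time point.

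**People who leave the study.** Section 12.1.1 defines study withdrawal as "any participant who does not complete the final follow-up visit or an early termination visit" and keeps their data for analysis up to the date they leave.

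**Schedule.** Under 9.3.3 the first doses are given on day 0. Participants in Arms A and B then take two more panobinostat doses at home, on days 2 and 4. Arm C has the day-0 injection only. The follow-up visits are on days 10 and 28.

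**The concern.** The plan asks for a day-10 sample from people who stop drug, defines an analysis set that contains them, and has a separate rule that throws the sample away. The rule acts on something that happens after randomization, and one arm cannot experience it. No sentence says which section prevails.

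Stage 3 is open-label with 10, 4 and 4 participants, so one or two people matter. An unresolved conflict leaves room to choose the set after results are known. If those who stop differ in their HIV-1 DNA change, dropping them from Arm B and not from Arm C makes the two groups no longer comparable as randomized.

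**Working it through.** **Step 1. Does the cut-off always reach the endpoint?** The last planned dose is on day 4 and the endpoint is on day 10. Someone who stops drug must do so before the day-2 or day-4 dose, so on the planned schedule the date of withdrawal always precedes day 10. For a stopper who attends day 10, the two sections give opposite answers: 14.4.3 includes the value and 12.1.2 discards it.

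**Step 2. Which arms?** On day 0, 9.3.3 says: "After the above procedures are completed, administer one s.c. dose of" PEG-IFN-α2a in Arms B and C. Arm C has nothing further to stop. Arms A and B do: they "will receive two more stage-specific panobinostat doses and will be instructed to take them in the mornings of study day 2 and day 4". The cut-off therefore acts in A and B only. B against C is exposed directly; B against A only if stopping differs between those two arms.

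**Step 3. The exclusion in 14.4.3.** Take a participant sampled on day 10 who leaves before day 28 without an early termination visit. The unlimited exclusion removes the day-10 value, while 12.1.1 keeps data up to departure. The virologic-failure limb can hardly apply by day 28: "HIV treatment failure is defined as a confirmed HIV-1 RNA increase to >400 copies/mL for more than 4 weeks".

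**Step 4. Reproduce the plan's power.** Inputs from 14.3: SD 0.436, difference 0.82 log10, 9 against 3 evaluable, one-sided rank-sum test, α = 0.05. There are C(12,3) = 220 rank arrangements. P(U ≤ 4) = 11/220 = 0.0500 and P(U ≤ 3) = 7/220 = 0.0318. Simulated normal data give 80% power when U ≤ 4 rejects, which matches the plan. Section 14.4.3 requires p strictly below 0.05, so U ≤ 3 applies and power is 72%. The strict rule is used below.

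**Step 5. False-positive rate, B against C.** Start from 10 against 4 with no true effect. The region is U ≤ 7, with 38/1001 = 3.8% when all are kept. The documents give no stopping rate, so the rates and shifts here are assumptions. Each participant is a would-be stopper with the stated probability, with DNA change shifted by the stated amount; stoppers are dropped from B only; the exact region is reset for the number remaining (400,000 simulations).

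| Stoppers' change | 5% stop | 10% | 20% | 30% |
|---|---|---|---|---|
| 1 SD worse | 4.6% | 5.2% | 6.6% | 8.1% |
| 0.5 SD worse | 4.2% | 4.5% | 5.0% | 5.5% |
| no different | 3.7% | 3.7% | 3.6% | 3.5% |
| 1 SD better | 3.3% | 2.8% | 2.1% | 1.5% |

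For B against A with equal stopping in both arms, the rate stays at 3.3%-3.8% throughout.

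**Step 6. Shift in the Arm B mean.** If k of 10 stoppers differ by 1 SD and are dropped, the mean moves by 0.436 × k/10. For k = 1 this is 0.044 log10 (1.11-fold); for k = 2 it is 0.087 log10 (1.22-fold). It can go in either direction.

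**Step 7. What keeping stoppers may cost.** Power at 0.82 log10 under the strict rule; half-responders have half the effect.

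| | 9 vs 3 | 10 vs 4 |
|---|---|---|
| No stoppers | 72% | 85% |
| One / two non-responders kept | 56% / 38% | 75% / 60% |
| One / two half-responders kept | 65% / 59% | 81% / 76% |
| One / two dropped from B | 75% / 69% | 84% / 82% |

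The 75% at 8 against 3 exceeds 72% because the attainable level rises from 0.0318 to 7/165 = 0.0424.

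**The case against.** **It may hardly ever happen.** This largely stands. The only scheduled post-dose safety checks before the third dose are the day-0 ECG and a call: "On Day 2, participants will be called by phone by one of the study investigators to discuss possible side effects". Section 14.4.2 expects low safety event rates. In the earlier panobinostat study summarised in 5.4.3.1, all 15 events likely related to drug were grade 1, although no interferon was given. Stopping rates of 20% or 30% have no support in the documents.

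**The inflation needs a special link.** This also stands. With no drug effect, stopping cannot itself change HIV-1 DNA, so tolerability and DNA change would have to be related for some other reason. Without such a link the rate stays at or below 3.8%.

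**The formal objective is B against A.** Section 4.1.2 names only that comparison. But the Schema, Hypothesis 2 in 5.6 and the co-primary endpoint in 14.1 all include Arm C, so B against C cannot be set aside.

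**Section 14.4.3 does not contradict itself.** A reader might infer that it does. An inclusion sentence followed by an exclusion sentence defines one set, so that inference fails. Section 14.3 speaks of unevaluable participants, which suggests that the exclusion was meant for people without a usable day-10 value. What remains is a missing time limit and tension with 12.1.1. None of this resolves 12.1.2, which concerns stopping drug and not leaving the study.

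**An on-treatment question is legitimate in a pilot, and withdrawn consent can justify a cut-off.** Both are fair. But the plan declares a modified intention-to-treat analysis, and the cut-off covers every trigger in 12.1.2, including adverse events in people who agreed to continue.

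**Conclusion.** Section 12.1.2 is wrong as written. Followed literally, it discards an observed primary endpoint after a post-randomization event that Arm C cannot have, and it conflicts with the analysis set in 14.4.3. The open-ended exclusion in 14.4.3 is a lesser matter that needs a time limit.

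The practical size is probably small and its direction is unknown. A reader might infer that the trial's error rate is inflated. The documents do not support that: exceeding 5% for B against C needs about 10% stopping with stoppers 1 SD worse, or more than 20% at 0.5 SD worse, and with equal stopping B against A is unaffected. Nor do they support analysing everyone with a day-10 value whatever their ART status, because 14.3 and 14.4.3 treat ART discontinuation as a reason for exclusion on purpose.

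This should be fixed, at the lower end of that category. Confidence is high on the conflict in the text and modest on its consequences.

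**What to change.** 1. In 12.1.2, state that participants withdrawn from drug who continue follow-up contribute all data from scheduled visits, including day 10, and are analysed as randomized under 14.4.3.
2. In 14.4.3, limit the exclusion to events before the day-10 sample. Leaving the study, going off ART or virologic failure after that sample then does not remove a valid value. Leave the exclusion for ART discontinuation before day 10 as it is.
3. State that 14.4.3 prevails over 12.1 for the efficacy analysis.
4. Report an analysis restricted to participants who completed study drug as a sensitivity analysis.

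The visits and assays are already scheduled, so the cost is wording. The statistical downside is dilution: with 9 against 3, power of 72% falls to 56% or 38% if one or two complete non-responders are kept. The gain is a single analysis set, fixed in advance, in which stopping drug does not remove a randomized participant; it is not a gain in power.

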#### 9.3.2 Screening/pre-entry phase

Once a candidate for study entry has been identified, the patient will be scheduled to meet with a study representative to discuss the study. If the patient decides to participate, s/he will sign the IRB-approved consent form. Subsequently, the participant will have a screening visit; this visit can occur immediately after signing the consent form.

During this screening visit (V1), the patient will be questioned regarding their medical history and will have laboratory testing performed to determine eligibility for the study. The following procedures will be performed:

- Obtain a medical history, including all information relevant to inclusion and exclusion criteria
- Review concomitant medications
- Perform a complete physical exam, including a non-mydriatic fundoscopic eye exam
- Perform a 12-lead ECG to calculate QTc intervals
- Schedule patient for a cardiac stress echocardiogram test (unless data already available)
- Obtain samples for screening laboratory tests:
  - Plasma HIV-1 RNA testing by Roche Taqman Version 2.0 assay.
  - CD4 T cell counts.
  - HIV antibody (if not previously documented).
  - TSH levels.
  - Urine HCG pregnancy test for female participants of childbearing potential.
  - PPD skin test or T spot TB test (unless data already available).
  - Hematology parameters and chemistry parameters as per Table 1.

If the candidate is eligible for the trial, he or she will return for one pre-entry visit. At this visit (V2), the following procedures will be performed:

[figure not shown]
- Pregnancy test (women of childbearing age).
- Other lab tests as indicated in Table 1.
- Collection of blood/serum for virological and immunological and gene expression assays.
- Immunogenetic studies for HLA class I and IL-28B genotyping.
- Record baseline level of diarrhea, nausea and vomiting that patients experience with their regular antiretroviral regimen.

Time	Screening/Pre-Entry		Treatment Phase				Post-Treatment Observation	
	≤-30d †	≤-10d †	D0 (0h)	D0 (6h)	D2	*D4 (6h)	D10	D28
Windows						+1	+/- 2	+/- 2
Amount Collected from Blood Draws (cc)	49	91	60	57		87	99	87
IFN- $\alpha$ 2a injection (Arm B and C only)			X					
Panobinostat (Arm A and B only)			X		X	X		
Visit numbers	V1	V2	V3			V4	V5	V6
Phone call for evaluation of AEs					X			
CBC 	X	X	X			X	X	X
HLA, KIR, IL-28b GT		X						
Liver function tests 	X					X		X
Chemistry 	X	X				X	X	X
TSH	X							

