### 14.4.3 Statistical analysis of virological and immunological data

The primary efficacy endpoint is the change from baseline to day 10 in the number of HIV-1 infected CD4 T cells, as assessed by proviral CD4 T cell-associated HIV-1 DNA levels determined on a log-scale. The null hypothesis of no difference in the primary efficacy endpoint between the randomized treatments will be tested using a one-sided Wilcoxon rank sum test. The null hypothesis will be rejected with a  $p < 0.05$ .

Changes in the frequency of HIV-1-infected CD4 T cells (determined by levels of CD4 T cell-associated proviral HIV-1 DNA) from baseline to completion of the treatment phase will also be summarized as secondary efficacy endpoints and compared between the two randomized treatments. Mean and quartile plots will be used to summarize these efficacy endpoints at each visit. If feasible with the modest sample size, longitudinal data methods will also be used to evaluate and estimate treatment effects.

Analysis for the primary efficacy endpoint will use a modified intent-to-treat analysis, limiting to participants who have received at least one dose of randomized treatment and have data at baseline and day 10. Participants who go off ART, experience virologic failure or discontinue study participation for other reasons will be excluded from the efficacy analysis. For this analysis, mixed models with repeated measures will be considered (MMRM). Missing data will be managed using guidelines defined by the National Research Council.

Primary safety endpoints will be tabulated by Cohorts and randomized treatments.

Analyses of secondary virologic and immunologic outcomes will parallel the primary analyses outline above.

Baseline immunologic and virologic parameters will be assessed at multiple pre-entry timepoints (see Table 1). For analysis of primary and secondary endpoints, the mean of multiple baseline assessments will be used.

Secondary analyses of all immunologic and virologic parameters stratified by genetic polymorphisms (in HLA and IL-28B genes) will also be carried out.

Associations between changes in the various virologic and immunologic measurements will be evaluated using scatterplots and correlation coefficients.

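### Section 12.1.2 keeps people who stop study drug in follow-up but cuts off their data at the stop date, in conflict with the day-10 analysis set in Section 14.4.3

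*Combined protocol and SAP*

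**What the plan says.** Section 12.1.2 deals with withdrawal from the investigational drug, which is "defined as a participant who discontinues study treatment but agrees to continue follow-up until completion of the study". Anyone who stops after one or more doses "will be asked to return for all subsequent study visits", and Section 9.5 gives the same encouragement. The closing paragraph of 12.1.2 then sets the data rule: "Participants withdrawn from the investigational drug will contribute with data for the statistical analyses until the date of withdrawal". Section 12.1.1, on leaving the study altogether, has a parallel sentence: "Participants withdrawn from the study will contribute with data for the statistical analyses until the date of withdrawal".

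Section 14.4.3 describes the primary efficacy set as modified intent-to-treat, "limiting to participants who have received at least one dose of randomized treatment and have data at baseline and day 10". It removes people who go off ART, people with virologic failure, and people who "discontinue study participation for other reasons will be excluded from the efficacy analysis". Stopping study drug is not on that list.

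On dosing, Section 9.3.3 says that at discharge on day 0 participants given panobinostat "will receive two more stage-specific panobinostat doses and will be instructed to take them in the mornings of study day 2 and day 4". By Table 1 those later doses exist only in Arms A and B. Arm C receives one injection on day 0 and nothing after it. The primary efficacy endpoint is the change in HIV-1 DNA to day 10.

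**The concern.** A cut-off at the date of leaving makes sense for someone who leaves the study. Applied to someone who has only stopped the drug and still attends, it throws away data that the protocol has deliberately collected. The day-10 value falls after any stop at dose 2 or dose 3, so the discarded value would be the primary efficacy outcome itself.

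Two things are at stake. First, the analysis set would depend on an event after randomisation that, on the scheduled days, can arise in Arms A and B but not in Arm C. That weakens the randomised comparison of B with C. Second, the efficacy comparison rests on stage 3, with 10, 4 and 4 participants. Section 7.4 replaces stage 3 dropouts only if they leave before the first dose, so a discarded participant is not made up.

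**Working it through.** **Tracing one participant through the text.** Take a stage 3 participant in Arm A or B who takes dose 1 on day 0, has a related grade 3 event before dose 2, stops under Section 11.3, and attends days 10 and 28.

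| Question | Section | Answer |
|---|---|---|
| Withdrawn from drug? | 12.1.2 | Yes: treatment stopped, follow-up continues |
| Withdrawn from the study? | 12.1.1 | No: the final visit is completed |
| Day-10 sample expected? | 12.1.2, 9.5 | Yes |
| Day-10 value usable? | 12.1.2, data rule | No: it comes after the stop date |
| In the primary efficacy set? | 14.4.3 | Yes: dosed, baseline and day 10 present |
| Caught by a 14.4.3 exclusion? | 14.4.3 | No: on ART, no virologic failure, still in the study |

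The references in 14.4.3 to MMRM and to missing-data guidelines do not resolve this, because the value is collected, not missing. A hold and restart for a grade 2 event under 11.2 is not a withdrawal and is unaffected.

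**A neighbouring case.** Someone who attends day 10 and leaves before day 28 has withdrawn from the study. Section 12.1.1 keeps their data to that date, which includes day 10, while 14.4.3 excludes people who discontinue participation. So the exclusion in 14.4.3 also disagrees with 12.1.1, and a repair must cover both cases.

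**Which comparison.** Arms A and B share the day-2 and day-4 doses, so the rule can act on either side of B versus A. In B versus C it can act, on schedule, only on B.

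**How many participants.** The documents give no rate of stopping drug and no outcomes for those who stop. Neither the number affected nor the size or direction of bias can be computed.

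**Illustration of small arms.** Inputs from Section 14.3: SD of change 0.436, effect 0.82 (both log10), 9 versus 3 evaluable, one-sided rank-sum test at 0.05. The test statistic U counts the pairs, one participant from each arm, in which the Arm B reduction is the larger. The null distribution was enumerated exactly, and power came from 400,000 simulated normal samples per case.

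- The plan's own figure: for 9 versus 3, rejecting at U of 23 or more has size 11/220 = 0.050 and power 0.80, which matches the stated 80%.
- Section 14.4.3 rejects at p below 0.05. Read strictly, that means U of 24 or more, size 7/220 = 0.032, power 0.72.

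Under the strict rule, for B versus A:

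| Analysed, B v A | Size | Power |
|---|---|---|
| 10 v 4 (all kept) | 38/1001 = 0.038 | 0.85 |
| 10 v 3 (one Arm A value lost) | 11/286 = 0.038 | 0.77 |
| 9 v 4 (one Arm B value lost) | 27/715 = 0.038 | 0.84 |
| 9 v 3 (the plan's allowance) | 7/220 = 0.032 | 0.72 |
| 9 v 2 (a second Arm A value lost) | 2/55 = 0.036 | 0.61 |
| 8 v 3 (a second Arm B value lost) | 7/165 = 0.042 | 0.75 |

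Power rises from 9 v 3 to 8 v 3 because the attained size jumps, so part of what moves these figures is the discreteness of the test. They also assume that a discarded participant's change is distributed like the rest of the arm.

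**The case against.** The best defence is that 14.4.3 is the specific section on the primary analysis and 12.1.2 is general termination text. The list of drug-withdrawal reasons in 12.1.2 includes loss of consent and study termination, where an end to data is natural, and the sentence looks carried over from 12.1.1. On that reading 14.4.3 governs and only the wording needs tidying. This is plausible, but no text says that 14.4.3 prevails, and 12.1.2 speaks of statistical analyses without limit.

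The window is also narrow, and this stands. The first dose is observed, and only two doses remain. Table 1 schedules no post-dose blood count, chemistry or liver test before day 4, six hours after the third dose, so scheduled laboratory results cannot stop a dose. The remaining routes include related grade 3 or 4 symptoms, hypersensitivity, participant request and starting an excluded drug. In the earlier panobinostat trial (Section 5.4.3), 15 people scheduled for 12 doses of 20 mg had only grade 1 events judged likely related. That trial gave no interferon, but Section 14.4.2 also expects low event rates.

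A reader might go further in three ways that the documents do not support.

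- *That adverse events after a drug stop drop out of the safety summary.* Sections 10.5.2 and 10.7 require later events to be reported and followed, 14.4.2 summarises events recorded as the protocol describes, and the escalation criteria in 10.9 count related events to day 28.
- *That power falls to 0.61.* That needs a second Arm A loss beyond the one unevaluable participant per arm already allowed in 14.3.
- *That B versus A carries the same built-in imbalance.* Both arms have the same later panobinostat doses.

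**Conclusion.** The inconsistency is real and touches the primary efficacy set. It is a stated rule that, if followed, discards day-10 outcomes already collected from participants who stop panobinostat before dose 2 or 3. On schedule this can happen only in Arms A and B, so it can bias B versus C, and it reduces arms that are already very small.

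The size is not known: the documents support no estimate of bias, few stops are expected, and the power figures only illustrate how little room the arms leave. Nothing suggests that the choice between the two rules would be made after seeing data; the point is that the text leaves it open. It should be settled before the analysis. The conclusion rests on reading a drug stop as distinct from discontinuing study participation, which is the distinction that 12.1.1 and 12.1.2 themselves draw.

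**What to change.** In Section 12.1.2, replace the data sentence with: 'Participants withdrawn from the investigational drug only will contribute data from all attended visits to the statistical analyses.'

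In Section 14.4.3, add: 'Participants who received at least one dose and have baseline and day-10 data are analysed in their randomised arm whether or not all doses were taken.' Make this subject to the exclusions for going off ART and for virologic failure, which stay. Limit the exclusion for discontinuing study participation to those who leave before the day-10 sample, so that it agrees with 12.1.1, which can stay as it is.

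The cost is three wording changes, with no new visits or samples, since these participants are already asked to attend. The downside is that estimates in Arms A and B would include people who missed panobinostat doses, so the Arm B effect may look slightly smaller. That is the usual price of analysing people as randomised.
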